10.9. COVID-19 Risk Assessment

DM can cause irreversible morbidity and even mortality, if untreated. As such, and due to the limited number of available treatment options, the benefit a participant may receive from joining an investigational study with a therapeutic treatment is potentially significant. Given that treatment for DM does involve immunosuppression, there is a theoretical concern that the risk for infection may be higher than in participants not receiving immunosuppressants. However, there is no specific data to further inform this risk. The site Investigator will therefore balance the risk/benefit considerations in the study participant taking these factors into account.

The potential risks identified and mitigation measures put in place in light of the COVID-19 pandemic are provided in Table 20.

Table 20: Potential Risks and Mitigation Measures Due to COVID-19

| Risks Category | Summary of Data/ Rationale for Risk | Mitigation Strategy |
|--|--|--|
| Potential risks | | |
| Healthcare institution availability for non-COVID-19-related activities | COVID-19 pandemic may impact the workload of healthcare institutions globally and may reduce staff availability to perform non-urgent activities and non-COVID-19-related activities. | During the time that the COVID19 pandemic is active, Alexion will only open study sites that report enough personnel capacity to sufficiently conduct clinical study related activities. |
| Data quality and integrity | Lack of availability of site personnel to perform study assessments and capture study specific data in a timely manner and to maintain adequate quality standards. Lack of availability of site personnel to ensure adequate and continuous chain of custody, storage conditions, and monitoring for investigational product and biological samples. Inability of study monitors and quality personnel to conduct in-person visits to exercise adequate oversight of study execution at investigational sites. Missing data (COVID19 pandemic may impact study visit schedules and increase missed visits and/or participant study discontinuations inadvertently resulting in missing data [eg, for protocol-specified procedures]). | During the time that the COVID19 pandemic is active, Alexion will only open study sites that report enough personnel capacity to sufficiently conduct clinical study related activities. During this timeframe, participants eligibility as well as site capacity will be reviewed by the site Investigator and the Alexion Medical Monitor or designee prior to Screening. Each site is also evaluated for the capacity to perform remote monitoring visits and remote source data verification. During the time that the COVID-19 pandemic is active, it will be important to capture specific information in the eCRF that explains the reason the data |

Table 20: Potential Risks and Mitigation Measures Due to COVID-19

| Risks Category | Summary of Data/ Rationale for Risk | Mitigation Strategy |
|----------------|--|--|
| | | are missing (eg, missed study visits or participant study discontinuations due to COVID-19). |

Abbreviations: COVID-19 = coronavirus disease 2019; eCRF = electronic case report form

10.10. COVID-19 Vaccine Risk Assessment

Following a review of the available COVID-19 vaccine data (eg, Pfizer/BioNTech, Moderna, AstraZeneca, Johnson & Johnson), it is unlikely that the immune response to a COVID-19 vaccine (and therefore the efficacy of the vaccination) would be diminished with concomitant ravulizumab administration, based on ravulizumab's mechanism of action. There is currently no information available evaluating the safety and efficacy of COVID-19 vaccines in participants treated with ravulizumab.

Vaccination may further activate complement. As a result, participants with complement-mediated diseases may experience increased signs and symptoms of their underlying disease. Therefore, participants should be closely monitored for disease symptoms after recommended vaccination.

Because vaccines may activate complement, if possible, consider vaccination when the underlying complement-mediated disease is clinically controlled and when systemic C5 inhibitor concentration (and subsequent complement blockade) is relatively high, shortly after administration.

Local and national guidelines should be consulted for recommendations related to COVID-19 vaccination.

The potential risks identified and mitigation measures put in place in light of the COVID-19 vaccination rollout are provided in Table 21.

Table 21: Potential Risks and Mitigation Measures Due to COVID-19 Vaccine

| Risks Category | Summary of Data/Rationale for Risk | Mitigation Strategy |
|----------------------------|---|---|
| Potential risks | | |
| Data quality and integrity | Missing data due to appointments for COVID-19 vaccination or side effects of COVID-19 vaccine may impact study visit schedules and increase missed visits and/or participant study discontinuations, inadvertently resulting in missing data (eg, for protocol-specified procedures). | Capture specific information in the eCRF that explains the reason the data is missing (eg, missed study visits due to appointments for COVID-19 vaccination or side effects of COVID-19 vaccine). |

Abbreviations: COVID-19 = coronavirus disease 2019; eCRF = electronic case report form

10.11. Abbreviations

The following abbreviations and terms are used in this study protocol.

Table 22: Abbreviations and Specialist Terms

| Abbreviation or Specialist Term | Explanation |
|---------------------------------|---|
| 30s CST | 30-second Chair Stand Test |
| ACR | American College of Rheumatology |
| ADA | antidrug antibody |
| AE | adverse event |
| AESI | adverse events of special interest |
| aHUS | atypical hemolytic uremic syndrome |
| ALT | alanine aminotransferase |
| anti-MDA5 | antimelanoma differentiation-associated protein 5 |
| anti-NXP2/MJ | antinuclear matrix protein 2 |
| AST | aspartate aminotransferase |
| C3 | complement component 3 |
| C5 | complement component 5 |
| C5a | complement component 5a |
| C5b | complement component 5b |
| C5b-9 | terminal complement complex |
| CDA-IGA | Cutaneous Dermatomyositis Activity Physician's Global Assessment |
| CDASI | Cutaneous Dermatomyositis Disease Area and Severity Index |
| CI | confidence interval |
| CIOMS | Council for International Organizations of Medical Sciences |
| CK | creatine kinase |
| COVID-19 | coronavirus disease 2019 |
| CRF | case report form |
| CSM | core set measure |
| CTCAE | Common Terminology Criteria for Adverse Events |
| DM | dermatomyositis |
| DMC | Data Monitoring Committee |
| DM-DSQ | Dermatomyositis Disease Symptoms Questionnaire |

Table 22: Abbreviations and Specialist Terms

| Abbreviation or Specialist Term | m Explanation | |
|---------------------------------|---|--|
| DSM | Diagnostic and Statistical Manual of Mental Disorders | |
| ECG | electrocardiogram | |
| eCRF | electronic case report form | |
| EDC | electronic data capture | |
| EOS | End of Study | |
| ePRO | electronic patient-reported outcome | |
| EQ-5D-5L | European Quality of Life Health 5-item questionnaire dimensions 5 level | |
| ET | Early Termination | |
| EULAR | European League Against Rheumatism | |
| FACIT | Functional Assessment of Chronic Illness Therapy | |
| FDA | Food and Drug Administration | |
| FSH | follicle-stimulating hormone | |
| GCP | Good Clinical Practice | |
| GDPR | General Data Protection Regulation | |
| GPS | Global Patient Safety | |
| gMG | generalized myasthenia gravis | |
| HAQ | Health Assessment Questionnaire | |
| HIPAA | Health Insurance Portability and Accountability Act | |
| HIV | human immunodeficiency virus | |
| HRT | hormone replacement therapy | |
| IB | Investigator's Brochure | |
| ICF | informed consent form | |
| ICH | International Council for Harmonisation of Technical Requirements for Pharmaceuticals for Human Use | |
| IDMC | Independent Data Monitoring Committee | |
| IEC | Independent Ethics Committee | |
| IMACS | International Myositis Assessment and Clinical Studies | |
| IMACS-TIS | International Myositis Assessment and Clinical Studies Total Improvement Score | |
| IRB | Institutional Review Board | |
| IRT | interactive response technology | |

Table 22: Abbreviations and Specialist Terms

| Abbreviation or Specialist Term | Explanation | |
|---------------------------------|--|--|
| IST | immunosuppressive/immunomodulatory therapy | |
| IV | intravenous(ly) | |
| IVIg | intravenous immunoglobulin | |
| LDH | lactate dehydrogenase | |
| mAb | monoclonal antibody | |
| MAC | membrane attack complex | |
| MDAAT | Myositis Disease Activity Assessment Tool | |
| MedDRA | Medical Dictionary for Regulatory Activities | |
| MITAX | Myositis Intention to Treat Activities Index | |
| MMT-8 | manual muscle testing subset of 8 muscles | |
| MRI | magnetic resonance imaging | |
| MYOACT | Myositis Disease Activity Assessment VAS | |
| NMOSD | neuromyelitis optica spectrum disorder | |
| NSAID | non-steroidal anti-inflammatory drug | |
| OLE | Open-Label Extension | |
| PD | pharmacodynamic(s) | |
| PK | pharmacokinetic(s) | |
| PNH | paroxysmal nocturnal hemoglobinuria | |
| PPS | Per Protocol Set | |
| PRO | patient-reported outcome | |
| PROMIS | Patient-Reported Outcomes Measurement Information System | |
| PT | physical therapy | |
| q8w | every 8 weeks | |
| RCP | Randomized Controlled Period | |
| SAE | serious adverse events | |
| SAP | Statistical Analysis Plan | |
| SC | subcutaneous | |
| SF-36 | Short Form Health Survey (36 questions version) | |
| SLE | systemic lupus erythematosus | |
| SoA | Schedule of Activities | |
| SOC | System Organ Class | |

Table 22: Abbreviations and Specialist Terms

| Abbreviation or Specialist Term | Explanation |
|---------------------------------|--|
| SS | Safety Set |
| SUSAR | suspected unexpected serious adverse reactions |
| TEAE | treatment-emergent adverse event |
| TESAE | treatment-emergent serious adverse event |
| TIS | total improvement score |
| TIS20 | ≥ 20-point improvement response on IMACS-TIS |
| TIS40 | ≥ 40-point improvement response on IMACS-TIS |
| TIS60 | ≥ 60-point improvement response on IMACS-TIS |
| ULN | upper limit of normal |
| VAS | visual analog scale |
| wGEE | weighted generalized estimating equation |
| WOCBP | woman of childbearing potential |

10.12. Protocol Amendment History

The protocol amendment summary of changes table for the current amendment is located directly before the Table of Contents.

| DOCUMENT HISTORY | | | |
|-------------------|--|-------------|--|
| Document | Type of Amendment (Global or Country-specific) | Date | Summary of Key Changes in the Amendment |
| Amendment 2.0 | Global | 30 Aug 2022 | To broaden the target population, reduce the risk of screen failures, improve patient experience, and to facilitate recruitment of participants. |
| Amendment 1.0 | Global | 27 Aug 2021 | To provide information on the IDMC, a clarification on Part A interim analysis, individual and study closure criteria. |
| Amendment 0.2 | UK | 10 Aug 2021 | To provide information regarding the IDMC, and to clarify interim analysis |
| Amendment 0.1 | Germany | 11 Aug 2021 | To introduce an IDMC and update study closure criteria |
| Original protocol | Not applicable | 07 May 2021 | Not applicable |

## **VERSION HISTORY**

This statistical analysis plan for ALXN1210-DM-310 is based on Protocol Amendment 3.0, dated 23 Jun 2023.

SAP Version	Version Date	Change	Rationale
1.0	20-August-2023	Not applicable	Original version

## **APPROVAL SIGNATURES**

## LIST OF ABBREVIATIONS

Abbreviation	Definition
ADA	antidrug antibody
AE	adverse event
AESI	adverse event of special interest
ATC	anatomic therapeutic class
CDA-IGA	Cutaneous Dermatomyositis Activity Physician's Global Assessment
CDASI	Cutaneous Dermatomyositis Disease Area and Severity Index
CI	confidence interval
COVID-19	coronavirus disease 2019
CSM	core set measures
CST	Chair Stand Test
CW	clinical worsening
DM	dermatomyositis
DPP	Data Presentation Plan
ECG	electrocardiogram
EQ-5D-5L	European Quality of Life Health 5-item questionnaire dimensions 5 level
FACIT-Fatigue	Functional Assessment of Chronic Illness Therapy – Fatigue Scale
HAQ	Health Assessment Questionnaire
HHD	handheld dynamometry
HR-QoL	health-related quality of life
IDMC	Independent Data Monitoring Committee
IE	intercurrent event
IMACS	International Myositis Assessment and Clinical Group
IMACS-TIS	International Myositis Assessment and Clinical Group - Total Improvement
	Score
LLOQ	lower limit of quantification
LOCF	last observation carried forward
LS	least square
MCS	mental component summary
MedDRA	Medical Dictionary for Regulatory Activities
MMT	manual muscle testing
NAb	neutralizing antibody
OLE	Open-Label Extension
PCS	physical component summary
PD	pharmacodynamics
PDAS	Pharmacodynamic Analysis Set
PK	pharmacokinetics
PKAS	Pharmacokinetic Analysis Set
PROMIS	Patient-Reported Outcomes Measurement Instrument System
PT	Preferred Term
QIC	Quasi-likelihood information criterion
QoL	quality of life
QTcF	QT interval corrected using Fridericia's formula
RCP	Randomized Controlled Period
SAE	serious adverse event
SAP	Statistical Analysis Plan

Abbreviation	Definition
SAS	Statistical Analysis Software
SF-36	Short Form Health Survey (36 Questions Version)
SOC	System Organ Class
SS	Safety Set
TEAE	treatment-emergent adverse event
TIS	Total Improvement Score
ULN	upper limit of normal
VAS	visual analog scale

## 1. INTRODUCTION

This statistical analysis plan (SAP) describes the statistical methods for analyzing data for Part A of Study ALXN1210-DM-310 Protocol Amendment 3.0, "A Phase 2/3, Double-blind, Randomized, Placebo-Controlled, Parallel Group, Multicenter Study to Evaluate the Efficacy and Safety of Ravulizumab in Adult Participants With Dermatomyositis." Standard data presentation instructions and table, figure, and listing specifications are contained in the Data Presentation Plan (DPP) in a separate document. The statistical methods for analyses of Part B will each be described in separate SAPs and associated DPPs.

The objective of Part A is to evaluate the efficacy and safety of ravulizumab compared with placebo after 26 weeks.

The primary efficacy analysis of Part A will be performed when the last participant in Part A completes the Week 26 Visit to conduct the analyses of the double-blind Randomized Controlled Period (RCP). At the time of the primary efficacy analysis, the Sponsor will be unblinded. Additional follow-up data for participants who have entered the Open-Label Extension (OLE) Period may be summarized, as relevant.

Changes to the protocol-planned analyses are described in Section 4.10.

## 1.1. Objectives, Endpoints, and Estimands

Objectives	Endpoints	
Primary		
To determine the effect of ravulizumab compared with placebo in the treatment of DM based on improvement in Total Improvement Score (TIS) IMAC-TIS	• TIS40 response at Week 26	
Secondary		
To assess the efficacy of ravulizumab compared with placebo in the treatment of DM based on improvement in efficacy endpoints	
 
TIS at Week 26
 
Change from Baseline in CDASI Activity Score at Week 26
 
Change from Baseline in 5 IMACS core set measures (extramuscular disease activity based on MDAAT, physician global activity assessment, patient global activity assessment, MMT-8, HAQ) at Week 26
 
Response related to muscle enzymes:         
 
normalization of most abnormal Baseline enzyme at Week 26
 
 
 
CDASI response (7-point improvement from baseline) at Week 26
 
CDA-IGA response (almost clear or clear) at Week 26
 
TIS20 response at Week 26
 
TIS60 response at Week 26
 
Time to first response of TIS20, TIS40, or TIS60, respectively
 
	

#### Table 1:Objectives and Endpoints

Table 1:	Objectives and Endpoints
----------	---------------------------------

Objectives	Endpoints
	
 
Clinical worsening during RCP at 2 consecutive visits
 
Receipt of acute therapy with standard DM treatment
 

Safety	
To characterize the overall safety of ravulizumab in participants with DM	• Incidence of treatment-emergent adverse events (TEAEs), treatment-emergent serious adverse events (TESAEs), and TEAEs leading to study intervention discontinuation
PK/PD/Immunogenicity	
To characterize the PK/PD and immunogenicity of ravulizumab in adult participants with DM	
 
Serum ravulizumab concentrations over the study duration
 
Change in serum free and total C5 concentrations over the study duration
 
Incidence and titer of ADA over the study duration
 

Exploratory	·
To evaluate the effect of ravulizumab on overall health-related quality of life (HR-QoL) and participant-centered and participant-reported outcomes in DM	
 
Change from Baseline in EQ-5D-5L at Week 26
 
Change from Baseline in PROMIS-29 v2.1 domains at Week 26
 
Change from Baseline in SF-36 at Week 26
 
Change from Baseline of DM symptoms captured
 

	
 
in DM-DSQ at Week 26
 
Change from Baseline in Patient Self-Assessment of Disease Activity (last question in the DM-DSQ) at Week 26
 

To evaluate, complement, inflammatory, autoimmune, and other soluble biomarkers in adult participants with DM	
 
Presence of myositis-specific autoantibodies (eg, anti-MDA5, anti-NXP2/MJ, and anti-synthetase/Jo-1, anti-TIF1) in blood, and change from Baseline in specific autoantibody/autoantibodies titer over the course of the study
 
Change from Baseline in plasma complement
 

	
 
activation (eg, sC5b-9, etc) over the course of the study
 
Change from Baseline in serum inflammatory markers (eg, IL6, etc) and other soluble markers (eg, KL6, etc) over the course of the study
 

To assess the efficacy of ravulizumab in the treatment of DM based on other efficacy endpoints	
 
Change from Baseline using scale to measure pruritus (5D-itch scale) at Week 26
 
Incidence of protocol-defined clinical worsening during RCP
 
Change from Baseline in handheld dynamometry performance at Week 26
 
Change from Baseline in 30-second Chair Stand Test (30s CST) at Week 26
 
Change from Baseline in FACIT-Fatigue at
 

#### **Primary Estimand**

The estimand is described by the following attributes:

- Population: Adult dermatomyositis (DM) participants who have an inadequate response or are intolerant to at least 1 DM treatment
- Endpoint: TIS40 response at Week 26
- Treatment: Ravulizumab versus Placebo
- Intercurrent events (IEs): Receipt of acute therapy with standard DM treatment or prohibited medications, and discontinuation of study intervention due to an AE or lack of efficacy or death during the RCP
  - Such IEs will be addressed via a composite strategy, where participants will be assumed to be TIS40 nonresponders (regardless of the observed TIS value) at all timepoints after first occurrence of either (1) receipt of acute therapy with standard DM treatment and/or prohibited medication, or (2) discontinuation of study intervention due to an AE or lack of efficacy or death
- Population-level summary: Difference in the percentage of TIS40 response between the ravulizumab and placebo arms

## 1.2. Study Design

Study ALXN1210-DM-310 is a Phase 2/3, double-blind, randomized, placebo-controlled, parallel group, multicenter study to evaluate the efficacy, safety, pharmacokinetics (PK), pharmacodynamics (PD), and immunogenicity of ravulizumab in adult participants with DM. The Phase 2 portion of the study is labeled as Part A.

Part A consists of 3 periods: Screening Period, RCP, and OLE Period. Participants will be screened for eligibility for up to 6 weeks during the Screening Period. Approximately 36 eligible participants will be randomized in a 2:1 ratio to receive weight-based intravenous infusion of either ravulizumab or placebo during the double-blind RCP. Upon completing the last assessment of the RCP at Week 26, participants may continue into the OLE Period.

For each participant, the RCP ends, and the OLE Period begins at Week 26. During the OLE Period, participants in the ravulizumab group will continue to receive ravulizumab treatment, and participants in the placebo group will switch to receive ravulizumab treatment. Participants will receive ravulizumab while in the OLE Period until ravulizumab is either registered or approved (in accordance with country-specific regulations) or for up to 130 weeks (approximately 2.5 years), whichever occurs first.

#### **Randomized Controlled Period**

All participants randomized into the study are expected to complete the RCP and will be followed up until the end of the RCP.

Participants who discontinue study intervention will complete the RCP. Participants who require acute therapy with standard DM treatment therapy due to protocol-defined clinical worsening (CW) and complete all remaining visits of the RCP will be permitted to enter the OLE Period.

Participants who discontinue/withdraw from the study will not be permitted to enter the OLE Period. Participants who will not enter the OLE Period will not receive an infusion at Week 26.

#### **OLE Period**

Participants completing the OLE Period in Part A will have an End-of-Study Visit at Week 156 and a follow-up phone call 21 weeks (± 1 week) after the participant's last dose of study intervention to collect information on concomitant medications, nonpharmacologic therapies and procedures, and AEs. Participants who discontinue study intervention will complete the visits and assessments of the OLE Period. Adjustments of "protocol allowed" DM medications will be permitted throughout the OLE Period. Participants who discontinue/withdraw from the study will complete an Early Termination Visit and a follow-up phone call.

An unblinded interim analysis for futility in Part A may be conducted when approximately 67% of participants have completed the Week 26 Visit or discontinued prematurely from the RCP of Part A. The unblinded interim analysis would be performed to assess futility by an Independent Data Monitoring Committee (IDMC). Details are provided in the IDMC Charter and the Interim Analysis Plan of Part A.

Participants from Part A of the study will not be enrolled in Part B (Phase 3) of the study, and therefore, will not contribute to the formal statistical hypothesis testing of Part B.

## 2. STATISTICAL HYPOTHESES

The null hypothesis associated with the primary endpoint is that there is no difference in TIS40 response rates between ravulizumab and placebo at Week 26 for Part A. The alternative hypothesis is that the response rates are different.

## 2.1. Multiplicity Adjustment

There will be no adjustment for multiplicity in Part A.

## **3. ANALYSIS SETS**

The analysis sets for Part A are defined as follows:

Population	Description
Screened Set	All consented participants.
Enrolled Set	All consented participants excluding screen failures.
Safety Set (SS)	All participants who receive at least 1 dose of the study intervention.
	Participants will be analyzed according to the study intervention they actually received.
Randomized Set	All randomized participants grouped by randomized treatment group.
Pharmacokinetic Analysis Set	All participants who receive at least 1 dose of the study intervention and who
(PKAS)	have at least 1 postdose PK sample.
Pharmacodynamic Analysis Set All participants who receive at least 1 dose of the study intervention at	
(PDAS)	have evaluable free or total complement component 5 data.
Immunogenicity Analysis Set	All participants who receive at least 1 dose of the study intervention and
	have at least 1 reportable ADA sample. Participants will be analyzed
	according to the study intervention they actually received.
OLE Set	All randomized participants who received at least 1 dose of ravulizumab
	starting from Week 26 onward.
All Ravulizumab-Treated Set	All participants who have received at least 1 dose of ravulizumab in the RCP
	and/or Open-Label Period.

## 4. STATISTICAL ANALYSES

#### 4.1. General Considerations

All data collected in this study will be presented separately by treatment arm and period (RCP, OLE) using summary tables, figures, and data listings. All analyses will be performed using Statistical Analysis Software® (SAS®) version 9.4 or higher (SAS Institute Inc., Cary, NC, USA) or other validated statistical software.

Summaries of study and participant characteristics (e.g., disposition, baseline characteristics and demographics, medical history, and protocol deviations, etc.) are described in Section 6.2.

All efficacy and safety analyses will be summarized for the RCP (up to Week 26) and the OLE Period. There may be additional summaries across the entire study period (RCP + OLE). The primary comparison will be ravulizumab treatment group versus the placebo treatment group during the RCP.

During the OLE Period, the participants who were randomized to placebo but later received ravulizumab will have additional variables created to reflect the data collected relative to the first dose of ravulizumab. At a minimum, all listings will include 2 sets of definitions for the following variables:

- Baseline value: Relative to the first randomized dose of placebo and relative to the first dose of ravulizumab in OLE.
- Study day: Relative to the first randomized dose of placebo and relative to the first dose of ravulizumab.
- Visit: Based on the actual study visit and visits re-aligned relative to the first dose of ravulizumab.

The descriptive analyses and presentations will be based on the types of variables being tested.

- 1. Overall summary of descriptive statistics for continuous variables will include but not limited to, number of observations, mean, standard deviation, median, minimum, and maximum, interquartile range, first quartile, and third quartile values. Minimum and maximum values will be reported to the same precision as the database.
- 2. Overall summary of descriptive statistics for categorical variables will include frequency counts and percentage of participants.

Formal statistical testing will be performed for the primary efficacy endpoint in the double-blind period. Testing will be conducted at the nominal 2-sided p-value of 0.20 level of significance.

Unless otherwise specified, data collected at any unscheduled visit and/or Early Termination will be included in by-participant listings, but not in the summary tabulations. However, unscheduled study visits will be used in the calculation of baseline values. Unscheduled visits/Early Termination visits will be included in the calculation of worst postbaseline values presented in shift tables.

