#### 4.6.3. Additional Safety Assessments

#### 4.6.3.1. Laboratory Parameters

Laboratory assessments are defined in the Protocol Section 10.3.

Clinical safety laboratory parameters will be expressed in standard international units. Laboratory data collected and recorded below lower limit of quantification (LLOQ) will be set to LLOQ for calculation of summary statistics (eg, < 400 U/L will be imputed as 400). Summaries will only include data analyzed from a central laboratory.

Summaries for each laboratory parameter (hematology, chemistry, coagulation, and urinalysis), which are continuous variables, will have a tabular summary of descriptive statistics at each scheduled visit. Descriptive statistics include actual value and change from Baseline at each scheduled visit.

Shift tables will be generated to summarize shifts from baseline categories to the worst postbaseline categories with directionality specified for any laboratory values, which could be reported in either direction (eg, above ULN or below ULN). Clinical laboratory tests with normal ranges will be classified as low, normal, and high. For these tests, abnormal values will be flagged in the listings with H when the value is higher than the upper limit of the reference ranges and with L when the value is lower than the lower limit of the reference ranges.

For hematology and chemistry laboratory values, summary tables of potentially clinically significant abnormalities will also be provided.

Separate listings of laboratory data collected from central compared and local laboratories will be generated. Out-of-range laboratory results will be identified in listings.

Boxplots will be presented over time by scheduled visit for planned chemistry and hematology parameters.

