#### 6.1.2. Visit Windows

For tables and figures, all summaries by timepoint during the RCP will be tabulated and analyzed per the scheduled visit as recorded on the electronic case reports forms (eCRF) even if the assessment is out of window. For shift table summaries, these will include unscheduled visits.

Unless otherwise specified, data collected at an unscheduled visit or Early Termination will be included in by-participant listing and/or spaghetti plots figures, but no assignment of the scheduled visit will be made for the purposes of tabulations. For the calculation of baseline, unscheduled visit will be considered. For shift tables, unscheduled visits or Early Terminations visits will be considered for worst post-baseline.

For the placebo participants who later receive ravulizumab during the OLE Period, an additional visit will be summarized. The Baseline will be remapped relative to ravulizumab (eg, Week 26 remapped to Day 1, and Week 28 relative to Week 2).

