## 6.5. Potentially Clinically Significant Criteria

Parameter	PCSA Low	PCSA High
Chemistry		
Potassium	< 3 mmol/L	$\geq$ 6 mmol/L
Calcium	< 1.75 mmol/L	> 3.4 mmol/L
Sodium	$\leq$ 129 mmol/L	$\geq$ 155 mEq/L
Blood urea nitrogen		> 40  mg/dL
Creatinine		> 186 umol/L
Total bilirubin		$> 2 \times ULN$
Alkaline phosphatase		$> 3 \times ULN$
AST		$> 3 \times ULN$
ALT		$> 3 \times ULN$
Albumin	$\leq$ 30 g/L	
Chloride	< 80 mmol/L	> 130 mmol/L
Glucose	< 3 mmol/L	
Hematology		
Hemoglobin	$\leq$ 115 g/L (male) $\leq$ 95 g/L (female)	$ \geq 185 \text{ g/L (male)}  \geq 165 \text{ g/L (female)} $
Platelets	< 100 10  /L	> 800 10  /L

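### The Part A tables of potentially clinically significant laboratory values omit unscheduled and Early Termination visits, because the SAP makes an exception for shift tables but not for them

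*SAP*

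**What the plan says.** SAP 4.1 sets the default. Unless otherwise specified, "data collected at any unscheduled visit and/or Early Termination will be included in by-participant listings, but not in the summary tabulations". Two exceptions follow. One concerns baseline: "However, unscheduled study visits will be used in the calculation of baseline values". The other is the only one for post-baseline data: "Unscheduled visits/Early Termination visits will be included in the calculation of worst postbaseline values presented in shift tables".

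SAP 6.1.2 repeats the arrangement. Unscheduled and ET data go to listings or spaghetti plots, and "no assignment of the scheduled visit will be made for the purposes of tabulations". Shift tables are again the exception: "For shift table summaries, these will include unscheduled visits".

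SAP 4.6.3.1 then plans a further laboratory output: "For hematology and chemistry laboratory values, summary tables of potentially clinically significant abnormalities will also be provided". It does not say which visits feed these tables. The cut-offs are in SAP 6.5, headed "Potentially Clinically Significant Criteria". Section 4.6.3.1 also restricts laboratory summaries to central-laboratory data. It describes the scale behind the shift tables as follows: "Clinical laboratory tests with normal ranges will be classified as low, normal, and high".

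**The concern.** A PCS table applies fixed cut-offs to every participant, independently of anyone's judgement about a given result. Its natural unit is the participant who ever crossed the cut-off after baseline. Under the SAP's default, these tables see scheduled visits only, although the protocol also draws safety laboratory samples at unscheduled and ET visits. A participant could cross a Section 6.5 threshold on a central-laboratory sample and still be reported as not having done so. With 24 and 12 participants per arm, a single omission visibly moves the percentage.

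**Working it through.** The point rests on which rule governs which output, so the sections are set side by side first. The arithmetic only gives the scale.

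**Step 1. Where an unscheduled or ET post-baseline laboratory value goes, and on what scale.**

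| Output | Uses unscheduled/ET values? | Scale | Source |
|---|---|---|---|
| By-visit descriptive summaries | No | Actual value and change | SAP 4.1, 6.1.2 |
| Shift tables, worst post-baseline | Yes | Low / normal / high | SAP 4.1, 6.1.2, 4.6.3.1 |
| PCS tables | No exception stated, so no | Section 6.5 cut-offs | SAP 4.6.3.1, 6.5 |
| Listings | Yes | H/L and out-of-range flags | SAP 4.1, 4.6.3.1 |
| Adverse event tables | Only if reported as an AE | Investigator judgement and grade | SAP 4.6.2; protocol 8.2.6 |

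Only the PCS row uses the Section 6.5 cut-offs, and the default excludes these visits from it.

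**Step 2. Can the shift table stand in?** No. It cannot separate a platelet count just below the reference range from one below 100 × 10⁹/L, or creatinine just above range from a value above 186 µmol/L. Transaminases are a particular case. AST and ALT are among the muscle enzymes that can support entry (at least 1.3 × ULN in inclusion criterion 7, at least 2 × ULN in criterion 8d). A participant who enters with raised ALT and passes 3 × ULN only at an unscheduled visit appears in the shift table as high to high, and in the PCS table not at all.

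**Step 3. Are samples taken at these visits?** Yes. Protocol Table 1 marks clinical laboratory tests in the unscheduled-visit column and in the Visit 6/ET column. The scheduled post-baseline visits in the Part A randomized period are Days 15, 71, 127 and 183, so after Day 15 they are 56 days apart (71 − 15 = 127 − 71 = 183 − 127 = 56). Protocol 7.1 calls for an unscheduled visit within a week when a decision to stop study intervention is made outside a study visit. Protocol 7.2 asks withdrawing participants for an ET visit 8 weeks after the last dose.

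**Step 4. Does the SAP widen visit scope elsewhere when it wants to?** Yes. SAP 4.6.3.3 summarizes notable ECG changes across all evaluations after treatment. The PCS sentence has no comparable wording.

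**Step 5. Scale.** The planned arm sizes are 24 ravulizumab and 12 placebo (protocol synopsis). For one participant whose only value meeting a given criterion falls at an unscheduled or ET visit, the loss in reported incidence is 1/n:

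- ravulizumab: 1/24 = 4.2 percentage points
- placebo: 1/12 = 8.3 percentage points

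The number of such participants is not given and cannot be derived from the documents.

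**The case against.** The strongest reply is that little of importance would be lost. Protocol 8.2.6 requires clinically relevant laboratory changes to be recorded as adverse events, and such events reach the TEAE, Grade 3 to 5 and discontinuation tables, which are not limited to scheduled visits. Every unscheduled and ET value is also listed, and with 36 participants a reader can scan the listings. Participants who stop study intervention stay in the study and keep attending scheduled visits, whose results are counted. An assessment made out of window but recorded under a scheduled visit is counted too. The tables are descriptive, no test or decision rule in these documents depends on them, and an IDMC monitors safety data.

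These points stand, and they limit the consequence. They do not close the gap. The adverse event route depends on judgement, and protocol 8.2.6 and 10.4.1 leave out findings attributed to the underlying disease unless they are more severe than expected. The listings flag values against the reference range, not against Section 6.5.

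A second reply is that the SAP places table specifications in a separate Data Presentation Plan, which could supply the missing rule. That is possible, and the plan is not among the documents. What can be shown is that the SAP does not state an exception and that its default points the other way.

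A reader might also infer that these values appear in shift tables and nowhere else. The documents do not support that: they also reach listings and possibly spaghetti plots, and unscheduled values can set baseline. The gap is confined to post-baseline summaries that use the Section 6.5 cut-offs.

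**Conclusion.** The point holds as a gap in the written rules. As the SAP stands, the PCS tables can understate incidence, by 4.2 points per affected ravulizumab participant and 8.3 per affected placebo participant. This assumes that the planned 24 and 12 are the denominators, that the Data Presentation Plan does not override the default, and that the participant has no other value meeting the same criterion at a scheduled visit.

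Two stronger readings are tempting and should not be drawn. One takes the 20% dropout assumption (0.20 × 36 = 7.2) to mean that about 7 participants would have results missing from these tables. That 20% is a sample-size allowance. It does not count unscheduled or ET samples, still less PCS values seen only there: many participants who stop treatment continue scheduled visits, the unscheduled stopping visit is conditional, and those lost to follow-up may give no ET sample. The other holds that PCS values are most likely to arise at these visits. Nothing in the documents shows this, and the repeat-testing rule in protocol 8.2.6 does not: a repeat follows a value already found, which is already counted if it came from a scheduled visit.

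This affects descriptive safety reporting only and leaves the efficacy analyses untouched. It is worth correcting because the correction is so small.

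**What to change.** Add one sentence to SAP 4.1 and 6.1.2, and mirror it in 4.6.3.1: *Shift tables and tables of potentially clinically significant abnormalities use all post-baseline central-laboratory values in the period, including those from unscheduled and Early Termination visits; in the latter tables each participant is counted once per criterion.*

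The limit to central-laboratory values is needed because 4.6.3.1 already excludes local results from summaries, and wording that admitted every post-baseline value would contradict it. Local-only results would stay out under either rule. It would also help to flag values meeting Section 6.5 in the laboratory listings and to align the Data Presentation Plan.

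The cost is a sentence in each section and a programming flag, with no new data collection.
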